8.4 Supply of Study Drug at the Site

Kits of ingenol mebutate 0.015% gel will be supplied to each subject at Baseline/Day 1. All subjects will be receiving the ingenol mebutate 0.015% gel, as there is no placebo control in this protocol.

8.4.1 Storage

Ingenol mebutate 0.015% gel should be stored by the study site in a refrigerator, 2 to 8°C (36 to 46°F). If the temperature of ingenol mebutate 0.015% gel storage in the clinic exceeds or falls below this range, this should be reported to Leo Pharma and captured as a deviation. Subjects will be instructed to store ingenol mebutate 0.015% gel in original packaging, in a refrigerator according to the instructions outlined on the Drug Administration Instructions.

Ingenol mebutate 0.015% gel tubes must be kept away from children at all times.

8.5 Study Drug Accountability

An accurate and current accounting of the dispensing and return of ingenol mebutate 0.015% gel tubes for each subject will be maintained on an ongoing basis by a member of the study site staff. The number of ingenol mebutate 0.015% gel tubes dispensed and returned by the subject will be recorded on the Investigational Drug Accountability Record.

8.6 Measures of Treatment Compliance

Subjects will be asked to keep a patient diary (on the Subject Instructions for Use sheet) noting their application of ingenol mebutate 0.015% gel. Subjects will be asked to bring their patient diary to Visit 4, to assess compliance.

9 STUDY PROCEDURES AND GUIDELINES

A Schedule of Events representing the required testing procedures to be performed for the duration of the study is diagrammed in Appendix 1.

Prior to conducting any study-related activities, written informed consent and the Health Insurance Portability and Accountability Act (HIPAA) authorization must be signed and dated by the subject or subject's legal representative. If appropriate, assent must also be obtained prior to conducting any study-related activities.

9.1 Clinical Assessments

9.1.1 Concomitant Medications

All concomitant medication and concurrent therapies will be documented at Screening and at Study Day 1, 4, 15, 29, 57, and at early termination (if applicable). Dose, route, unit frequency of administration, and indication for administration and dates of medication will be captured.

9.1.2 Demographics

Demographic information (date of birth, gender, race) will be recorded at Screening.

9.1.3 Medical History

Relevant medical history, including history of current disease, other pertinent respiratory history, and information regarding underlying diseases will be recorded at Screening.

9.1.4 Physical Examination

A complete physical examination will be performed by either the investigator or a subinvestigator who is a physician at Screening and at Day 1, 29, and early termination (if applicable). New abnormal physical exam findings must be documented and will be followed by a physician or other qualified staff at the next scheduled visit.

9.1.5 Actinic Keratoses (AK) count

An AK count will be performed to count the lesions in the treatment area. AK count will be performed at Screening, Day 1, Day 29, Day 57, and early termination (if applicable).

9.1.6 Local Skin Response (LSR)

LSR is measured by visual assessment by the investigator using a 4 point scale on 6 responses for a maximum total of 24. The points are assessed using the LSR scale (Appendix III) : The 6 responses are: Erythema, Flaking/Scaling, Pustulation/Vesiculation, Crusting, Swelling, and Erosion/Ulceration. The mean maximum LSR composite score and trend in score over the study visits will be reported as descriptive data and compared to historical controls. LSR assessment will performed at every visit.

9.1.7 Visual Analog Scale (VAS) Pain Assessment

Patients will be asked to rate their pain on a VAS numeric pain distress scale where 0 = no pain, 5 = moderate pain, 10 = unbearable pain. The (VAS) Numeric Pain Distress scale will be administered on Day 1, Day 4, Day 15, Day 29, Day 57, and early termination (if applicable).

9.1.8 Skindex-16

Skindex-16 is used to measure quality of life in patients with skin diseases. The Skindex-16 will be administered on Day 1, Day 4, Day 15, Day 29, Day 57, and early termination (if applicable).

9.1.9 Photography

The investigator or trained study staff will photograph the subject's treatment area on Day 1, Day 4, Day 15, Day 29, Day 57, and early termination (if applicable). Prior to photographing the treatment area, study staff will (1) photograph a subject identification card including: subject's initials, subject number, visit day and date; and (2) place a light-balanced sticker in the treatment area.

9.1.10 Adverse Events

Information regarding occurrence of adverse events will be captured throughout the study. Duration (start and stop dates and times), severity/grade, outcome, treatment and relation to study drug will be recorded on the case report form (CRF).

9.2 Clinical Laboratory Measurements

Clinical laboratory measurements will be performed at Screening, Day 4, Day 29, and early termination (if applicable). If a subject's medical record contains hematology and blood chemistry profile results within 14 days of Screening, the existing values may be used and Screening laboratory measurements are not required. If a subject's medical record contains hematology and blood chemistry profile results within 5 days of Day 29, the existing values may be used and additional laboratory measurements are not required.

9.2.1 Hematology

Blood will be obtained and sent to each site's clinical hematology lab for a complete blood count (hemoglobin, hematocrit, red blood cell count, white blood cell count, white blood cell differential, and platelet count).

9.2.2 Blood Chemistry Profile

Blood will be obtained and sent to the site's clinical chemistry lab for determination of serum sodium, potassium, chloride, bicarbonate, random glucose, BUN, creatinine, aspartate aminotransferase (AST/SGOT), alanine aminotransferase (ALT/SGPT).

9.2.3 Pregnancy Test

A urine pregnancy test will be obtained from female subjects who are of childbearing age prior to their participation in the study, and at Day 1.

9.2.4 Urinalysis

Not applicable.

10 EVALUATIONS BY VISIT

The following is a list of evaluations scheduled to occur at each visit. Screening and Visit 2 visits can occur on the same day.

10.1 Visit 1 (Screening, Day -14 to 1)

1. Review the study with the subject and obtain written informed consent and HIPAA authorization.
2. Assign the subject a unique screening number.
3. Record demographics data.
4. Record medical history, including a history of actinic keratosis, diagnosis date, and prior actinic keratosis treatments.
5. Record concomitant medications.
6. Perform a complete physical examination.

7. Perform an actinic keratosis count.
8. Collect blood for clinical laboratory tests (chemistry and hematology).
9. Collect urine sample and perform urine pregnancy test (if applicable).
10. Continue to Visit 2 procedures (can occur on the same day), or schedule subject for Visit 2/ Day 1.

10.2 Visit 2 (Day 1)

1. Record any Adverse Events.
2. Concomitant medications review.
3. Perform a complete physical examination.
4. Perform an actinic keratosis count.
5. Perform a local skin response assessment.
6. Subject to perform a VAS pain assessment.
7. Subject to complete the Skindex-16.
8. Perform photography in treatment area.
9. Collect urine sample and perform urine pregnancy test (if applicable).
10. Dispense a kit of ingenol mebutate 0.015% gel; subject will complete the first application under the investigator's supervision in the clinic.
11. Dispense subject 2 additional kits for use on Day 2 and Day 3. Subject will also be provided with a detailed application instructions hand-out.
12. Schedule subject for Visit 3/ Day 4.

10.3 Visit 3 (Day 4)

1. Record any Adverse Events.
2. Record changes to concomitant medications.
3. Review subject diary for compliance.
4. Perform a local skin response assessment.
5. Subject to perform a VAS pain assessment.
6. Subject to complete the Skindex-16.
7. Perform photography in treatment area.
8. Collect blood for clinical laboratory tests (chemistry and hematology).
9. Schedule subject for Visit 4/ Day 15.

10.4 Visit 4 (Day 15)

1. Record any Adverse Events.
2. Record changes to concomitant medications.

3. Perform a local skin response assessment.
4. Subject to perform a VAS pain assessment.
5. Subject to complete the Skindex-16.
6. Perform photography in treatment area.
7. Schedule subject for Visit 5/ Day 29.

10.5 Visit 5 (Day 29)

1. Record any Adverse Events.
2. Record changes to concomitant medications.
3. Perform complete physical examination.
4. Perform an actinic keratosis count.
5. Perform a local skin response assessment.
6. Subject to perform a VAS pain assessment.
7. Subject to complete the Skindex-16.
8. Perform photography in treatment area.
9. Collect blood for clinical laboratory tests (chemistry and hematology).
10. Schedule subject for Visit 6/ Day 57.

10.6 Visit 6 (Day 57)

1. Record any Adverse Events.
2. Record changes to concomitant medications.
3. Perform an actinic keratosis count.
4. Perform a local skin response assessment.
5. Subject to perform a VAS pain assessment.
6. Subject to complete the Skindex-16.
7. Perform photography in treatment area.

10.7 Early Termination Visit (if required)

1. Record any Adverse Events.
2. Record changes to concomitant medications.
3. Perform complete physical examination.
4. Perform an actinic keratosis count.
5. Perform a local skin response assessment.
6. Subject to perform a VAS pain assessment.

7. Subject to complete the Skindex-16.
8. Perform photography in treatment area.
9. Collect blood for clinical laboratory tests (chemistry and hematology).
10. Collect urine sample and perform urine pregnancy test (if applicable).

11 ADVERSE EXPERIENCE REPORTING AND DOCUMENTATION

11.1 Adverse Events

An adverse event (AE) is any untoward medical occurrence in a clinical investigation of a patient administered a pharmaceutical product and that does not necessarily have a causal relationship with the treatment. An AE is therefore any unfavorable and unintended sign (including an abnormal laboratory finding), symptom or disease temporally associated with the administration of an investigational product, whether or not related to that investigational product. An unexpected AE is one of a type not identified in nature, severity, or frequency in the current U.S. package insert or of greater severity or frequency than expected based on the information in the U.S. package insert.

The Investigator will probe, via discussion with the subject, for the occurrence of AEs during each subject visit and record the information in the site's source documents. Adverse events will be recorded in the patient CRF. Adverse events will be described by duration (start and stop dates and times), severity, outcome, treatment and relation to study drug, or if unrelated, the cause.

AE Severity

The National Cancer Institute's Common Terminology Criteria for Adverse Events (CTCAE) Version 3.0 should be used to assess and grade AE severity, including laboratory abnormalities judged to be clinically significant. The modified criteria can be found in the study manual. If the experience is not covered in the modified criteria, the guidelines shown in Table 1 below should be used to grade severity. It should be pointed out that the term "severe" is a measure of intensity and that a severe AE is not necessarily serious.

Table 1. AE Severity Grading

Severity (Toxicity Grade)	Description
Mild (1)	Transient or mild discomfort; no limitation in activity; no medical intervention or therapy required. The subject may be aware of the sign or symptom but tolerates it reasonably well.
Moderate (2)	Mild to moderate limitation in activity, no or minimal medical intervention/therapy required.
Severe (3)	Marked limitation in activity, medical intervention/therapy required, hospitalizations possible.
Life-threatening (4)	The subject is at risk of death due to the adverse experience as it

	occurred. This does not refer to an experience that hypothetically might have caused death if it were more severe.
--	--

AE Relationship to Study Drug

The relationship of an AE to the study drug should be assessed using the following the guidelines in Table 2.

Table 2. AE Relationship to Study Drug

Relationship to Drug	Comment
Definitely	Previously known toxicity of agent; or an event that follows a reasonable temporal sequence from administration of the drug; that follows a known or expected response pattern to the suspected drug; that is confirmed by stopping or reducing the dosage of the drug; and that is not explained by any other reasonable hypothesis.
Probably	An event that follows a reasonable temporal sequence from administration of the drug; that follows a known or expected response pattern to the suspected drug; that is confirmed by stopping or reducing the dosage of the drug; and that is unlikely to be explained by the known characteristics of the subject's clinical state or by other interventions.
Possibly	An event that follows a reasonable temporal sequence from administration of the drug; that follows a known or expected response pattern to that suspected drug; but that could readily have been produced by a number of other factors.
Unrelated	An event that can be determined with certainty to have no relationship to the study drug.

11.2 Serious Adverse Experiences (SAE)

An SAE is defined as any AE occurring at any dose that results in any of the following outcomes:

- death
- a life-threatening adverse experience
- inpatient hospitalization or prolongation of existing hospitalization
- a persistent or significant disability/incapacity
- a congenital anomaly/birth defect

Other important medical events may also be considered an SAE when, based on appropriate medical judgment, they jeopardize the subject or require intervention to prevent one of the outcomes listed.

11.2.1 Serious Adverse Experience Reporting

The study site will document all SAEs that occur (whether or not related to study drug) per [UCSF CHR Guidelines](#). The collection period for all SAEs will begin after informed consent is obtained and end after procedures for the final study visit have been completed.

In accordance with the standard operating procedures and policies of the local Institutional Review Board (IRB)/Independent Ethics Committee (IEC), the site investigator will report SAEs to the IRB/IEC.

12 DISCONTINUATION AND REPLACEMENT OF SUBJECTS

12.1 Early Discontinuation of Study Drug

A subject may be discontinued from study treatment at any time if the subject, or the investigator feels that it is not in the subject's best interest to continue. The following is a list of possible reasons for study treatment discontinuation:

Subject withdrawal of consent

Subject is not compliant with study procedures

Adverse event that in the opinion of the investigator would be in the best interest of the subject to discontinue study treatment

Protocol violation requiring discontinuation of study treatment

Lost to follow-up

Positive pregnancy test (females)

If a subject is withdrawn from treatment due to an adverse event, the subject will be followed and treated by the Investigator until the abnormal parameter or symptom has resolved or stabilized.

All subjects who discontinue study treatment should come in for an early discontinuation visit as soon as possible and then should be encouraged to complete all remaining scheduled visits and procedures.

All subjects are free to withdraw from participation at any time, for any reason, specified or unspecified, and without prejudice.

Reasonable attempts will be made by the investigator to provide a reason for subject withdrawals. The reason for the subject's withdrawal from the study will be specified in the subject's source documents Refer to Section 10 for early termination procedures.

12.3 Withdrawal of Subjects from the Study

A subject may be withdrawn from the study at any time if the subject or the investigator feels that it is not in the subject's best interest to continue.

All subjects are free to withdraw from participation at any time, for any reason, specified or unspecified, and without prejudice.

Reasonable attempts will be made by the investigator to provide a reason for subject withdrawals. The reason for the subject's withdrawal from the study will be specified in the subject's source documents. As noted above, subjects who discontinue study treatment early (i.e., they withdraw prior to Visit 6) should have an early discontinuation visit. Refer to Section 10 for early termination procedures. Subjects who withdraw after

Visit 2 but prior to Visit 6 should be encouraged to come in for a final visit (and the procedures to be followed would include those for their next scheduled visit).

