4 STUDY DESIGN

4.1 Study Overview

This is a single arm, open-label interventional study of ingenol mebutate 0.015% in solid organ transplant recipients. Twenty subjects are planned; 10 kidney transplant recipients and 10 lung transplant recipients. These populations have been selected as they represent the spectrum of solid organ transplantation: kidney transplant recipients are the largest transplant population, but have lower levels of immunosuppression and skin cancer risk. Lung transplant recipients have the highest burden of skin cancer and actinic keratoses.

Screening data will be reviewed to determine subject eligibility. Subjects who meet all inclusion criteria and none of the exclusion criteria will be enrolled into the study.

The following treatment regimens will be used:

- Experimental treatment: Ingenol mebutate 0.015%, topical gel
- Placebo or Comparator: None

Total duration of subject participation will be 57 days. Total duration of the study is expected to be 8 months.

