12.4 Replacement of Subjects

Subjects who withdraw from the study treatment will not be replaced.

Subjects who withdraw from the study will not be replaced.

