15.4 Analysis of Secondary Endpoints

Safety and tolerability data will be summarized by each secondary endpoint.

The mean maximum LSR composite score, the VAS score, and the Skindex-16 scores and trend in scores over the study visits will be reported as descriptive data. The composite LSR score will be compared to historical controls (Lebwohl et al, NEJM 2012).

The efficacy analysis will be based on the intent-to-treat (ITT) population. In the ITT population, patients will be counted in the treatment group upon informed consent, and receipt of at least one dose of study medication.

For efficacy analysis, all missing values due to patient early termination from the study will be imputed using last observation carried forward (LOCF) method, as appropriate. For each patient, the Baseline values will be defined as those values recorded at Day 1 prior to dosing or Screening as appropriate. Patients who are lost-to-follow-up after Baseline will be included to the ITT population carrying forward their Baseline values, i.e., these patients will be considered as treatment failures.

Percent reduction in number of actinic keratoses and proportions of patients with partial and complete clearance of actinic keratoses will be presented descriptively and visualized as histograms. These scores will be compared to historical controls (Lebwohl et al, NEJM 2012).

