15.6 Sample Size and Randomization

This is a pilot descriptive sample, not powered for analysis. The sample size of 20 patients is selected to achieve a reportable sample size in two subgroups of organ transplant recipients.

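### Last observation carried forward has no minimum time after treatment, so an early-termination AK count taken before Day 29 can stand as the Day 57 clearance result

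*Combined protocol and SAP*

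**What the plan says.** Section 15.4 sets the missing-data rule for efficacy, and the synopsis repeats it: "all missing values due to patient early termination from the study will be imputed using last observation carried forward (LOCF) method, as appropriate". Neither place says when a count qualifies to be carried. The next sentences of 15.4 treat subjects lost to follow-up after Baseline differently: their Baseline values are carried and they count as treatment failures.

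Section 10.7 lists the early-termination procedures. Item 4 is "Perform an actinic keratosis count", with no minimum time since dosing. Section 9.1.5 and Appendix 1 also place an AK count at early termination. Otherwise they schedule counts only at Screening, Day 1, Day 29 and Day 57, so there is none at Day 4 or Day 15.

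Section 12.3 deals with withdrawal. Subjects who leave before Visit 6 are to have an early discontinuation visit: "Refer to Section 10 for early termination procedures". It then says that subjects who leave between Visit 2 and Visit 6 should be encouraged to attend a final visit, where "the procedures to be followed would include those for their next scheduled visit".

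**The concern.** Two subjects who leave a few days after dosing can be classified in opposite ways. One attends an early-termination visit, and the count made that day may be carried to Day 57. The other does not return and is a failure by rule. The difference comes from attendance and timing, not from lesion status eight weeks after treatment.

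There is reason to doubt that a count made so early measures the same thing as a Day 57 count. Section 2.1 says local reactions typically start on day 1. The scale in Appendix III grades scaling, crusting, pustulation and erosion over more than half of the treated area. Partial clearance depends on AKs that can be seen clinically. Exclusion criterion 5 accepts that skin disease in the field could interfere with evaluating AKs. The first scheduled post-treatment count is at Day 29.

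At stake are percent reduction, partial clearance and complete clearance. All three are compared with historical controls under 15.4, in a sample where one subject is 5% of the total.

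**Working it through.** **Inputs**

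- Sample size, Section 4.1: "Twenty subjects are planned; 10 kidney transplant recipients and 10 lung transplant recipients". Check: 10 + 10 = 20, which agrees with Section 15.6.
- Section 15.6: "This is a pilot descriptive sample, not powered for analysis". No alpha, power, effect size or dropout rate is given, so there is no sample-size formula to reproduce.
- Section 12.4: "Subjects who withdraw from the study will not be replaced".
- Partial clearance, Section 5.2: at least a 75% reduction at Day 57. Complete clearance has no day attached in 5.2; Day 57 is assumed here.
- Baseline count, Section 6.2: 4 to 20 lesions.

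**Step 1. Which count reaches Day 57, by time of withdrawal**

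| Subject leaves | Next scheduled visit | AK count if 10.7 is followed | AK count if only the next-visit list is done | Value carried to Day 57 |
|---|---|---|---|---|
| After Visit 2, before Visit 3 | Day 4 | Yes | No | Early count, or Baseline |
| After Visit 3, before Visit 4 | Day 15 | Yes | No | Early count, or Baseline |
| After Visit 4, before Visit 5 | Day 29 | Yes | Yes | Termination count on either reading |
| After Visit 5, before Visit 6 | Day 57 | Yes | Yes | Termination count on either reading |

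The carry-forward of a pre-Day-29 count can arise in the first three rows. The ambiguity in 12.3 affects AK collection only in the first two.

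**Step 2. What the carried value does to response**

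A subject is a partial responder if the carried count is at most 0.25 × Baseline: 0.25 × 4 = 1 lesion, or 0.25 × 20 = 5 lesions. Take a subject with 4 lesions at Baseline and 1 at an early-termination visit. Carrying the early count gives (4 − 1)/4 = 75%, a responder. Carrying Baseline gives (4 − 4)/4 = 0%, a non-responder.

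**Step 3. Size per subject**

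With k reclassified subjects, a clearance proportion moves by k/20:

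- k = 0: 0 points
- k = 1: 5 points
- k = 2: 10 points
- k = 3: 15 points

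For each reclassified partial responder, mean percent reduction moves by 75/20 = 3.75 to 100/20 = 5 points. If clearance were shown by organ type, one subject would be 1/10 = 10 points. However, Section 15.3 provides for separate subgroup reporting only for adverse events.

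**Step 4. Scale**

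An observed 10/20 is 50% (exact 95% interval 27.2 to 72.8). An observed 11/20 is 55% (31.5 to 76.9). One reclassified subject is small beside the sampling uncertainty, but it is a shift in the point estimate that the plan could avoid.

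**The case against.** A reader might infer that 10.7 and 12.3 contradict each other and that any early dropout's result depends on which one is followed. The text does not support that. Section 12.3 itself sends withdrawals to Section 10, and its sentence on the next scheduled visit is inclusive, not exclusive. Read together, the two lists add up and the AK count is always taken. What remains is loose wording inside 12.3: it names an early discontinuation visit and a final visit without saying whether they are the same. The AK consequence is limited to withdrawals before Visit 4.

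A reader might also infer that inflammation hides lesions and so inflates efficacy in those who tolerated treatment worst. No section says that early counts are unreliable, when reactions end, or why Day 4 and Day 15 have no count. Local skin response is graded at Day 29 and Day 57 as well, so grading alone does not mark out the early period. Redness or scale could also be miscounted as lesions. The direction is plausible, not shown.

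A link to the primary safety endpoint is tempting too, because laboratory values feed its first component. It is weak. The Day 4 list includes a draw, and a subject leaving between Visits 3 and 4 should already have that one. Section 10.6 and Appendix 1 give completers no Day 57 draw, though Section 5.3 lists one.

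Other points on that side stand. Section 12.1 encourages those who stop treatment to complete the remaining visits, so many would have a true Day 57 count. The rule is qualified, and Section 15 promises a detailed SAP before the final analysis. Replacing the carried count with Baseline is an analysis choice that sets percent change to 0. None of this supplies the missing limit: the qualifier in 15.4 is undefined, and the cumulative reading of 12.3 guarantees an early count without restricting its use.

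**Conclusion.** The point holds for the carry-forward rule. As written, an AK count made at any time after dosing may be used as the Day 57 value, and a dropout can be a responder on that basis while a subject lost after Baseline is a failure. The 12.3 wording is a lesser ambiguity.

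The size is 5 points of clearance per affected subject. With an assumed 0 to 3 such subjects the shift is at most 0 to 15 points. This is an upper bound: each must leave before Day 29, attend a termination visit, have no later count, and meet the response threshold on that early count. Zero is compatible with the documents. The calculation takes all 20 planned subjects as the denominator.

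The endpoints are secondary and descriptive, and no test depends on them. The change is worth making because it is cheap and the results will be set against historical controls.

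**What to change.** 1. In Section 15.4 and the synopsis, state that an early-termination AK count taken before Day 29 is reported but not carried to Day 57. Such subjects take their Baseline count and are non-responders, as already laid down for subjects lost after Baseline. This uses the protocol's own first scheduled post-treatment count and its own failure convention. The cost is a sentence in each place, and clearance and mean percent reduction may be slightly less favourable.

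2. As a clarification, state in Section 12.3 that the 10.7 list applies to every withdrawal visit. This adds no assessment that 10.7 does not already require. Once item 1 is in place, both readings of 12.3 make withdrawals before Visit 4 non-responders, so item 2 serves complete collection of AK, examination and laboratory data. Item 2 without item 1 would secure the early count but leave it free to be carried forward.
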